12.2 Secondary Effectiveness Analyses

The secondary effectiveness endpoints are as follows:

1. Patient survival at Day 30 post-transplantation
2. Incidence of severe primary graft dysfunction (PGD) (left or right ventricle) in the first 24 hours post-transplantation
3. Rate of donor hearts utilization that were successfully transplanted after preservation and assessment on the OCS™ heart device

These endpoints will be summarized using frequencies and percentages and exact (Clopper-Pearson) 95% confidence intervals for the true population percentages. The first two secondary effectiveness endpoints will be analyzed based on the Transplanted Recipient Population (Table 4.1). The third endpoint, which is the ratio of the number of successfully transplanted donor hearts divided by the number of donor hearts in the OCS™ Heart Population, will be analyzed based on the OCS™ Heart Population (Table 4.1).

12.3 Other Effectiveness Analyses

The composite endpoint, patient survival at day 30 post-transplantation and within initial hospital discharge and absence of severe PGD (left or right ventricle) in the first 24 hours post-transplantation, will be summarized (Table 4.2) overall and by individual component using counts and percentages and an exact (Clopper-Pearson) 95% confidence interval for the true population percentage.

Table 4.3 will present Kaplan-Meier estimated survival time probabilities for the following nominal time points: Day 30, Month 6, and Month 12.

13.0 SAFETY ANALYSES

13.1 Adverse Events

Only serious adverse events and heart graft-related adverse events will be reported.

Safety will be analyzed principally by examination of the frequency of adverse events. In particular, the number of heart graft-related serious adverse events (SAEs) in the first 30 days post-transplantation per subject will be analyzed. This endpoint is defined to consist of the following adverse events (at most one per type), if they are serious adverse events:

- Moderate or severe Primary Graft Dysfunction (PGD) (left or right ventricle) (not including rejection or cardiac tamponade):. Please see Appendix 2 of the protocol for detailed definitions of LV and RV PGD according to ISHLT consensus manuscript.
- Primary graft failure requiring re-transplantation

This endpoint will be summarized using descriptive statistics and a 95% confidence interval for the mean based on the t-distribution (Tables 6.1).

In addition, the numbers and percentages of subjects experiencing at least one serious adverse event (AE), at least one heart graft-related AE, at least one severe heart graft-related AE, at least one device-related heart graft-related AE (AEs that are probably or definitely related to the investigational device or for which the relationship is missing), at least one unanticipated heart graft-related AE, and at least one heart graft-related serious AE, and the number and percentage of deaths will be tabulated (Table 6.2). Also, the number of heart graft-related AEs and the number and percentage of subjects experiencing heart graft-related AEs will be tabulated by system organ class (SOC) and preferred term (PT) using MedDRA (Table 6.3). Similarly, the number of SAEs and the number and percentage of subjects experiencing SAEs will be tabulated by system organ class (SOC) and preferred term (PT) using MedDRA (Table 6.4), and the number of heart graft-related serious AEs and the number and percentage of subjects experiencing heart graft-related serious AEs will be tabulated by SOC and PT using MedDRA (Table 6.5). The number and percentage of heart graft-related AEs will be tabulated by SOC and PT and the relationship of the adverse event to the device (related versus not related, where AEs with a probable or definite relationship to the investigational device are classified as related, and AEs with a possible, unlikely, or unrelated relationship are classified as not related) (Table 6.6) and by SOC and PT and severity (Table 6.8). The number and percentage of subjects experiencing heart graft-related AEs will be tabulated by SOC and PT and the relationship of the adverse event to the device (related versus not related) (Table 6.7) and by SOC and PT and severity (Table 6.9).

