The primary effectiveness endpoint will be summarized using counts and percentages and an exact 95% confidence interval for the true percentage based on the binomial distribution. A one-sided exact binomial test at the 0.05 significance level will be performed to test the null hypothesis H_0 .

The secondary effectiveness endpoints for this trial are as follows:

- Patient survival at day-30 post-transplantation
- Incidence of severe primary heart graft dysfunction (PGD) (left or right ventricle) in the first 24 hours post-transplantation
- Rate of donor hearts utilization from above characteristics that were successfully transplanted after preservation and assessment on the OCSTM heart device.

Each secondary effectiveness endpoint will be summarized using counts and percentages and an exact 95% confidence interval for the true percentage based on the binomial distribution.

Safety

Safety will be analyzed principally by examination of the frequency of adverse events. In particular, the number of heart graft-related serious adverse events (SAEs) up to the 30-day follow-up after transplantation per subject will be analyzed. This endpoint is defined to consist of the following adverse events (at most one per type), if they are serious adverse events:

- Moderate or severe primary heart graft dysfunction (PGD) (left or right ventricle) (not
 including rejection or cardiac tamponade). Please see Appendix 2 for detailed definition of LV
 and RV PGD according to ISHLT consensus manuscript.
- Primary graft failure requiring re-transplantation.

This endpoint will be summarized using descriptive statistics, specifically the mean, median, standard deviation, minimum, maximum, and a 95% confidence interval for the mean based on the t-distribution.

Determination of Sample Size

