4.3. Safety Endpoint

Incidence of heart graft-related Serious Adverse Events (SAEs) in the first 30 days post heart transplantation, defined as:

 Moderate or Severe Primary heart graft dysfunction (PGD) (left or right ventricles) (not including rejection or cardiac tamponade). Please see Appendix 2 for detailed definition of LV and RV PGD according to ISHLT consensus manuscript. Primary graft failure requiring re-transplantation

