9.4. Analysis of Safety

Safety will be analyzed principally by examination of the frequency of adverse events. In particular, the number of donor heart graft-related serious adverse events (SAEs) up to the 30-day follow-up after transplantation per subject will be analyzed. This endpoint is defined to consist of the following adverse events (at most one per type), if they are serious adverse events:

- Primary heart graft dysfunction (not including rejection or cardiac tamponade):
 - Use of ECMO, RVAD, LVAD, BiVAD or insertion of a new IABP for >12 hours post TX.
 - Use of ≥ 2 inotropic agents/vasopressors including high-dose epinephrine or norepinephrine for >7 days post heart TX.
 - Open chest post heart TX. due to compromised heart function
- Primary graft failure requiring re-transplantation

This endpoint will be summarized using descriptive statistics. A 95% confidence interval for the mean based on the t-distribution will be presented.

This endpoint will be analyzed based on the transplanted recipient population.

In addition, the numbers and percentages of subjects experiencing at least one heart graft-related AE, at least one (definitely or probably-related) device-related AE, at least one unanticipated AE, and at least one serious AE, and the number and percentage of deaths will all be tabulated. Also, the number of heart graft-related adverse events and the number and percentage of subjects experiencing adverse events will be tabulated by system organ class and preferred term using MedDRA. A similar analysis will be performed for serious AEs. AEs will also be tabulated at the event level by system organ class and preferred term and the relationship of the adverse event to the device using counts and percentages. Similar analyses will be performed by the severity of the adverse event.

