3.4 Determination of Sample Size

The sample size for this trial was determined based on the primary effectiveness composite endpoint of patient survival at Day 30 post-transplantation and absence of severe primary graft dysfunction (PGD) (left or right ventricle) in the first 24 hours post-transplantation. The primary statistical hypotheses to be tested are as follows:

$$H_0: \pi \leq 0.65 \quad \text{and}$$

$$H_1: \pi > 0.65,$$

where π is the true proportion of transplanted recipients with patient survival at day 30 post-transplantation and absence of severe PGD (left or right ventricle) in the first 24 hours post-transplantation. A one-sided exact binomial test will be performed to test the null hypothesis. The sample size calculations assumed an alpha level of 0.05, a Performance Goal of 0.65, a true primary endpoint proportion for OCSTM of 0.80, and power of 80%. Based on these specifications, the required sample size was determined to be 55 transplanted recipients. Assuming that there are exactly 55 transplanted recipients in the study, the null hypothesis will be rejected only if at least 76.4% (i.e., 42 of the 55 recipients) meet the primary endpoint. In order to increase the statistical power, the sample size was increased to 75 transplanted recipients.

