4.4 Safety Endpoint

The safety endpoint is the number of heart graft-related serious adverse events in the first 30 days post-transplantation per subject. This endpoint is defined to consist of the following adverse events (at most one per type), if they are serious adverse events:

- Moderate or severe Primary Graft Dysfunction (PGD) (left or right ventricle) (not including rejection or cardiac tamponade). Please see Appendix 2 of the protocol for detailed definitions of LV and RV PGD according to ISHLT consensus manuscript.
- Primary graft failure requiring re-transplantation.

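### The safety endpoint is a per-recipient count capped at one per event type, but it gets a t-interval for a mean; an exact interval for the proportion affected would be better calibrated on the upper side

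*SAP*

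**What the plan says.** SAP 4.4 defines the endpoint as a count: "The safety endpoint is the number of heart graft-related serious adverse events in the first 30 days post-transplantation per subject". SAP 13.1 caps it: "This endpoint is defined to consist of the following adverse events (at most one per type), if they are serious adverse events". Two types follow: moderate or severe primary graft dysfunction (PGD), and primary graft failure leading to re-transplantation.

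For the analysis, SAP 13.1 states: "This endpoint will be summarized using descriptive statistics and a 95% confidence interval for the mean based on the t-distribution (Tables 6.1". Protocol 9.4 agrees: "A 95% confidence interval for the mean based on the t-distribution will be presented". The safety paragraph of the protocol synopsis also specifies "a 95% confidence interval for the mean based on the t-distribution".

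Protocol 4.3 names the endpoint differently: "Incidence of heart graft-related Serious Adverse Events (SAEs) in the first 30 days post heart transplantation, defined as".

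Elsewhere the SAP uses exact binomial intervals: for the primary endpoint when no data are missing and for its by-site results (12.1), for the three secondary endpoints (12.2), and for the composite in Table 4.2 (12.3). Table 6.2 will give the number and percentage of recipients with at least one heart graft-related serious adverse event, with no interval stated.

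**The concern.** A t-interval is symmetric and takes its width from the sample standard deviation. If re-transplantation rarely accompanies a counted PGD event (an inference, since the documents do not say), nearly all scores are 0 or 1. The mean is then close to a proportion, and its standard deviation shrinks as the observed proportion falls. Samples with few events therefore give intervals that are both low and narrow, so the error collects at the upper limit.

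The trial has one arm and no comparator. The upper limit is the natural reading of how much graft-related harm remains compatible with the data, and it is the side on which this interval is least reliable.

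The rest of the plan does not supply a substitute. Table 6.2 has no stated interval and counts a wider class, because protocol 8.1 defines heart graft-related events by any untoward effect tied to the function of the transplanted heart. The exact interval for severe PGD in the first 24 hours leaves out moderate PGD and re-transplantation.

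**Working it through.** **Inputs.** SAP 3.4 gives n: "the required sample size was determined to be 55 transplanted recipients", and then "In order to increase the statistical power, the sample size was increased to 75 transplanted recipients". I use n = 75, with n = 55 as a check. The documents state no expected rate or target precision for the safety endpoint, so true rates of 5-20% are an assumption. Each recipient is scored 0 or 1.

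**The plan's own figure.** The only calculated figure nearby is the primary sample size. An exact binomial calculation with n = 55, a goal of 0.65, a true rate of 0.80 and rejection at 42 or more successes gives one-sided alpha 0.0489 and power 0.8032, so the plan's figure is reproduced. It says nothing about safety precision. It does give a scale: a planned success rate of 0.80 implies about 20% with death by Day 30 or early severe PGD.

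**Formulas.** With x affected recipients and m = x/n, the t-interval is m ± t × sqrt(m(1 − m)/(n − 1)), where t is the 97.5% point on n − 1 degrees of freedom (1.9925 for n = 75). The comparator is Clopper-Pearson. Coverage is the sum of binomial probabilities over every x whose interval contains the true rate.

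**One case in full, x = 15.** m = 0.20; sqrt(0.16/74) = 0.0465; 1.9925 × 0.0465 = 0.0927. The interval is 10.7% to 29.3%, against an exact 11.65% to 30.83%.

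| Affected of 75 | t-interval (%) | Clopper-Pearson (%) | Upper-limit gap (points) |
|---|---|---|---|
| 0 | 0 to 0 | 0 to 4.80 | 4.8 |
| 1 | −1.32 to 3.99 | 0.03 to 7.21 | 3.2 |
| 3 | −0.54 to 8.54 | 0.83 to 11.25 | 2.7 |
| 4 | 0.13 to 10.54 | 1.47 to 13.10 | 2.6 |
| 10 | 5.46 to 21.21 | 6.58 to 23.16 | 1.9 |
| 11 | 6.47 to 22.86 | 7.56 to 24.73 | 1.9 |
| 15 | 10.73 to 29.27 | 11.65 to 30.83 | 1.6 |

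**Long-run behaviour at n = 75 (nominal coverage 95%, nominal upper-side miss 2.5%).**

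| True rate | t coverage | t upper limit below truth | Clopper-Pearson upper limit below truth | P(3 or fewer events) |
|---|---|---|---|---|
| 5% | 89.0% | 10.6% | 2.1% | 48% |
| 10% | 94.3% | 5.0% | 1.6% | 5% |
| 15% | 93.2% | 5.4% | 2.3% | 0.24% |
| 20% | 94.0% | 5.0% | 2.4% | 0.007% |

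At n = 55, t-interval coverage at 10%, 15% and 20% is 91.5%, 91.7% and 93.4%, with upper-side misses of 7.7%, 7.0% and 5.8%.

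**If some recipients score 2.** With 10 affected of 75, one of them counted twice, the t-interval for the mean is 5.6 to 23.7 events per 100 recipients. It is still symmetric, and it is not an interval for the proportion affected.

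**The case against.** **The endpoint is defined as a number per recipient, so a mean estimates what was defined.** This stands as far as it goes and is why the mean should be kept. It does not make a t-interval well calibrated on such data, and protocol 4.3 still calls the endpoint an incidence.

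**The 0/1 reading is not guaranteed.** This also stands. Under the same cap, Appendix 2 numbers moderate left-ventricular, severe left-ventricular and right-ventricular PGD separately, and protocol 9.4 lists a different set of PGD components. On those readings one recipient might count more than once, and the coverage figures above would not carry over directly.

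**Part of the gap comes from Clopper-Pearson itself.** True: at rates of 10-30% it covers 95.6-96.8%. Against the Wilson upper limit (30.41% at 15/75) the gap falls to 30.41 − 29.27 = 1.1 points. The 5% upper-side miss at rates of 10-20% does not depend on the comparator, though it falls to 3.5% at a rate of 30%.

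**The table shells are not reproduced, so the layout of Table 6.1 cannot be judged.** True, but the text of SAP 13.1 names only descriptive statistics and the t-interval.

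A reader might go further in three ways, which the documents do not support:
- That the interval will generally collapse to zero width or run below zero. At n = 75 this needs 3 or fewer events. No rate is stated, and at rates near the 20% failure scale of the primary endpoint it would almost never happen.
- That every other proportion in the SAP has an exact interval. With missing primary data the plan is multiple imputation with a normal-approximation test; survival over time is Kaplan-Meier; adverse-event percentages have no stated interval.
- That a trial decision is at risk. The safety endpoint has no hypothesis, goal or success rule, and the stopping rule in protocol 14.10 uses deaths. Day-30 survival and severe PGD have their own exact intervals.

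**Conclusion.** The point holds as a matter of reported precision. At assumed true rates of 10-20% with 75 recipients scored 0 or 1, the planned interval covers about 93-94%, its upper limit is roughly 1.5 to 2 points below the exact one, and that limit is too low about twice as often as stated (about 5% against 2.5%). At a 5% rate the shortfall is larger: 89% coverage and a 10.6% upper-side miss. An interval of [0, 0] or a negative lower limit arises only with 3 or fewer events.

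This rests on three assumptions: the event rate, which the documents do not give; scores of mostly 0 or 1, which follows from the two types in SAP 13.1 only if both seldom occur in one recipient; and about 75 recipients analysed. The change is worth making because the error lies on the side that understates harm and the SAP already uses the remedy elsewhere.

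**What to change.** In SAP 13.1 and Table 6.1, report the number and percentage of recipients with at least one safety-endpoint event, and with each listed type, with Clopper-Pearson 95% limits. Keep the mean count per recipient as a descriptive figure, and remove the t-interval from SAP 13.1, protocol 9.4 and the synopsis.

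State what counts as one type, and reconcile SAP 13.1, protocol 9.4 and Appendix 2 so that the count and the proportion rest on the same list.

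The cost is document wording and a small programming change, with no new data. The headline moves from a mean count to a proportion affected, so the text should say so. The interval will be slightly wider and somewhat conservative: at 15/75, 11.65% to 30.83% in place of 10.73% to 29.27%.

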8. EVALUATION OF ADVERSE EVENTS

8.1. Evaluation of Heart Graft-Related Adverse Events

Heart Graft-Related Adverse Events are those which have any untoward effect on the health or safety of the patient and that are related to the transplanted heart function (except for acute rejection or myocardial tamponade). Heart graft-related adverse events will be collected from the time a subject is transplanted with a heart preserved on OCSTM until the completion of the 30-day follow-up evaluation. A heart graft-related adverse event will be followed until resolution or stabilization of the event.

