8.5. Recording and Reporting of Adverse Event

All heart graft-related adverse events and serious adverse events are to be recorded on the electronic case report forms until post-transplant day 30. The description of the adverse event will include: the date of onset, duration, severity, seriousness, the relationship of the event to the trial treatment, anticipated or not, and any treatment required. All serious adverse events occurring during the course of the first 30 days post-transplant will be reported to TransMedics, Inc., as well as documented on the appropriate electronic case report form(s). For all SAEs, the investigator is required to supply any additional data that may be deemed necessary by the Sponsor. Additionally, any serious adverse events (SAE) and unanticipated adverse device effects (UADE) should be reported to TransMedics, Inc., preferably within 48 hours of the time the investigator learns of the event, but in no case later than 5 working days. Heart graft-related AEs will be recorded up to the 30-day follow-up or through hospital discharge if longer than 30 days. For any particular patient, the Independent Medical Monitor if required to protect patient safety may specify a different follow-up period. The Sponsor is responsible for the classification and reporting of heart graft-related adverse events to the appropriate regulatory authorities, and for the on-going safety evaluation of the trial in accordance with ISO 14155 and governing regulatory requirements.

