3.5 Changes to the Protocol-Specified Analyses

No changes were made to the protocol-specified analyses.

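### SAP 13.1 limits the device-related, unanticipated and relationship tabulations to heart graft-related events, a limit that Protocol 9.4 does not set and SAP 3.5 does not declare

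*SAP*

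**What the plan says.** Protocol 9.4 lists several subject-level counts as separate items. The first is subjects with a heart graft-related AE. The next are "at least one (definitely or probably-related) device-related AE, at least one unanticipated AE, and at least one serious AE". Only the first carries the graft-related limit. The same section asks for AEs at event level by system organ class (SOC), preferred term (PT) and relationship to the device, again without the limit.

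SAP 13.1 defines the matching rows of Table 6.2 as "at least one device-related heart graft-related AE (AEs that are probably or definitely related to the investigational device" or have no relationship recorded) and "at least one unanticipated heart graft-related AE". For Table 6.6 it states: "The number and percentage of heart graft-related AEs will be tabulated by SOC and PT and the relationship of the adverse event to the device". Table 6.7 does the same at subject level. Table 6.4 covers all SAEs, by SOC and PT only.

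Protocol 8.1 confines the heart graft-related class to untoward effects "related to the transplanted heart function (except for acute rejection or myocardial tamponade"). Protocol 8.5 records, for each event, "the relationship of the event to the trial treatment, anticipated or not, and any treatment required". SAP 3.5 says: "No changes were made to the protocol-specified analyses".

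**The concern.** The heart graft-related class is a subset of what the trial records. If the device-related and unanticipated counts are taken only within that subset, a serious event that the investigator attributes to OCS preservation, but not to the function of the transplanted heart, drops out of both the count and the relationship tables. A reader of Table 6.2 could then see no device-related events while the database holds one.

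This matters more than usual because the trial has a single arm. Without a concurrent control, the causality assessment is one of the few tabulated ways to separate harm from the device from the background of heart transplantation. Protocol 10.1 names previously unknown side effects as the device's own risk, and the unanticipated row is where a reader would look for them. Because SAP 3.5 declares no change, the reader has no warning that the rows are narrower than the protocol promised.

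**Working it through.** The documents give no figure to reproduce for this point. The check is a comparison of text, followed by one piece of arithmetic.

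**Step 1: match each protocol item to its SAP table.**

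| Item | Protocol 9.4 | SAP 13.1 |
|---|---|---|
| Subjects with a device-related event | any AE judged definitely or probably related | Table 6.2: heart graft-related AEs only |
| Subjects with an unanticipated event | any AE | Table 6.2: heart graft-related AEs only |
| Events by relationship to device | AEs by SOC and PT | Table 6.6 (and 6.7, by subject): heart graft-related AEs only |
| Subjects with a serious event | any SAE | Table 6.2: any SAE, no relationship or anticipated status |
| SAEs by SOC and PT | yes | Table 6.4: all SAEs, no relationship or anticipated status |

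The table titles in the SAP's list of tables confirm the limit for 6.6 and 6.7.

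**Step 2: establish what is recorded.** The opening sentence of Protocol 8.5 could be read as covering only graft-related SAEs. A later sentence of the same section requires all SAEs in the first 30 days to be reported and entered on the case report form. SAP 13.1 settles the matter: it reports SAEs and heart graft-related AEs, and it separates Table 6.4 (all SAEs) from Table 6.5 (graft-related SAEs). Non-graft SAEs are therefore expected in the database, with relationship and anticipated status. Non-serious, non-graft AEs are not collected.

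**Step 3: identify the affected set.** Let G be the heart graft-related AEs and S all SAEs. The recorded events are G together with S. The SAP counts device-related and unanticipated events within G only, so the set left out is S outside G, that is, the non-graft SAEs. For such an event judged definitely device-related or unanticipated:

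- relationship or device-related tabulations that include it (6.2 row, 6.6, 6.7): 0;
- unanticipated tabulations that include it (6.2 row): 0;
- other output that includes it: the any-SAE row of Table 6.2, Table 6.4, and Listings 11.1 and 11.2.

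**Step 4: direction and size.** G is contained in the recorded events, so restricting to G can lower a count but never raise it. If d subjects have their only device-related (or only unanticipated) events among the non-graft SAEs, the row is short by d/n. At the planned maximum of n = 75:

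- d = 1: 1/75 = 1.3 percentage points;
- d = 2: 2/75 = 2.7 percentage points;
- d = 3: 3/75 = 4.0 percentage points.

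The values of d are illustrative. Nothing in the documents allows d to be estimated. A subject who also has a graft-related device-related event is already in the Table 6.2 row, so for that subject only Tables 6.6 and 6.7 lose information.

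**The case against.** The strongest reply is that nothing is hidden. Every non-graft SAE counts in the any-SAE row and in Table 6.4. SAP 5.1 puts all collected data in the listings, so relationship and anticipated status can be read there. Outside the tables, the Medical Monitor reviews SAEs and their classification as device-related (Protocol 14.9), the DSMB sees the safety data (14.10), and unanticipated adverse device effects have their own reporting route (8.5 and 13.2). The items are descriptive. Protocol 9.4 also mixes the terms for graft-related and general adverse events in its SOC and PT sentence, so some narrowing may have been meant as clarification. Finally, the SAP counts a missing relationship as device-related in Table 6.2, which is conservative.

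Most of this stands, and it limits the weight of the point. It does not remove it. The protocol specified tabulations, which a listing does not replace. The mixed wording is not in the device-related, unanticipated or relationship items. The rule for missing relationship works only inside the graft-related class.

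Two stronger readings are tempting, and the documents do not support them. A reader might sort the anticipated events in Protocol 8.3 by name and infer that most of them, such as renal dysfunction or respiratory failure, can never reach the relationship tables. Protocol 8.1 defines the class by cause, not by organ, so such an event qualifies if it is attributed to poor function of the transplanted heart; only acute rejection and tamponade are excluded by name. That list also says nothing about unanticipated events. A reader might also infer that all adverse events outside graft function are lost. The non-serious ones are never collected, so the SAP wording cannot have removed them.

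**Conclusion.** The point holds for non-graft SAEs. As written, SAP 13.1 leaves any such event that is judged device-related or unanticipated out of every device-related, relationship and unanticipated tabulation. This departs from Protocol 9.4, and the statement in SAP 3.5 is incorrect for these items. The restriction by itself can only understate the counts, by 1.3 percentage points per affected subject at n = 75. How many subjects would be affected is unknown.

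The conclusion rests on reading the unqualified items of Protocol 9.4 as unrestricted and on non-graft SAEs being recorded with both attributes. The primary test, the sample size and the designated safety endpoint (Table 6.1) are unchanged. This should be corrected before the analysis, but it does not threaten the trial's main conclusion.

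**What to change.** In SAP 13.1:

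- Define the device-related and unanticipated rows of Table 6.2 on all recorded events, meaning all SAEs plus heart graft-related AEs, and keep the graft-related rows as subsets beneath them.
- Add relationship to OCS to Table 6.4, or run Tables 6.6 and 6.7 on all SAEs plus heart graft-related AEs.
- If any narrowing is kept, declare it in SAP 3.5 with the reason.

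The cost is SAP wording, table shells and a little programming; the data are already collected. The reported device-related counts may come out slightly less favourable.

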8.6. Relationship of an Adverse Events to OCS™ Heart

The investigator will assess the relationship of the AE to the OCSTM Heart or to the standard of care, methods of preservation. The relationship will be assessed using the following categories:

- **Definitely Related:** There is a reasonable causal and temporal relationship between preservation with the OCSTM Heart and the adverse event.
- **Probably Related:** It is more likely than not that there is a reasonable causal relationship between preservation with the OCSTM Heart the adverse event.

- **Possibly Related:** There is a reasonable relationship with preservation with the OCSTM Heart and the adverse event, but the causal relationship is unclear or lacking.
- **Unlikely Related:** There is a temporal relationship with preservation with the OCSTM Heart and the adverse event, but there is not a reasonable causal relationship between the trial device and the event.
- **Unrelated:** There is no relationship between preservation with the OCSTM Heart and the adverse event.

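### SAP 13.1 labels possibly related adverse events as not related in Tables 6.6 and 6.7, and its rule for a missing relationship covers Table 6.2 only

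*SAP*

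**What the plan says.** Protocol 8.6 has the investigator rate relationship as definite, probable, possible, unlikely or unrelated. It defines possibly related as follows: "There is a reasonable relationship with preservation with the OCSTM Heart and the adverse event, but the causal relationship is unclear or lacking".

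Protocol 9.4 uses relationship in two places. One is a count of subjects with "at least one (definitely or probably-related) device-related AE". The other is an event-level table by system organ class, "preferred term and the relationship of the adverse event to the device using counts and percentages". Neither place mentions missing ratings, and the second states no grouping of categories.

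SAP 13.1 uses relationship in three tables:

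- **Table 6.2** (subjects with at least one device-related event) counts "AEs that are probably or definitely related to the investigational device or for which the relationship is missing".
- **Table 6.6** (events) has two classes. Definite and probable ratings count as related. For the other three ratings the rule is that "AEs with a possible, unlikely, or unrelated relationship are classified as not related".
- **Table 6.7** (subjects) uses the same related/not related split.

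Missing ratings are not mentioned for Tables 6.6 and 6.7. SAP 3.5 declares no changes to the protocol-specified analyses.

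**The concern.** The trial is single-arm, and protocol 3.1 says a concurrent control is not possible. Graft dysfunction after transplant of an expanded-criteria heart may come from the donor organ, the operation or the preservation. With no comparison rate, the relationship rating is one of the few planned ways to separate these sources. Possible is a likely rating when more than one cause is plausible. A table that puts it in the same column as unlikely and unrelated no longer shows how many events were uncertain.

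A second problem is internal consistency. One section gives a rule for missing ratings in one table and none for the two tables that break down the same kind of events. What is at stake is how these descriptive tables read, not the primary test.

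**Working it through.** The documents give no figure on this point, so the check starts with the text.

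**Step 1: class given to each rating**

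| Rating | Protocol 9.4 subject count | SAP Table 6.2 row | SAP Tables 6.6 and 6.7 |
|---|---|---|---|
| Definite | device-related | device-related | related |
| Probable | device-related | device-related | related |
| Possible | not counted | not counted | not related |
| Unlikely | not counted | not counted | not related |
| Unrelated | not counted | not counted | not related |
| Missing | not stated | device-related | not stated |

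Three things follow.

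1. The cut between probable and possible comes from the protocol, for the subject count.
2. The two-class reduction of the event-level relationship table (6.6), and the label given to possible events there, appear only in the SAP. Table 6.7 is a subject-level counterpart that protocol 9.4 does not spell out.
3. The missing-as-related rule appears only in the SAP, and only for Table 6.2.

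**Step 2: does the label fit the definition?** Under protocol 8.6, unlikely means no reasonable causal relationship, and unrelated means no relationship at all. Possible means a reasonable relationship with causality unclear or lacking. That describes uncertainty, so placing it under not related turns it into a negative finding.

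**Step 3: how far could the figures move?** The inputs are assumptions: 75 subjects (the maximum in SAP 3.1; the analysed number may be smaller), each in one category, with counts chosen for illustration. Let *d* be subjects rated definite or probable, *p* possible and *m* missing.

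- Table 6.2 row as planned: (*d* + *m*)/75
- Table 6.7 related row as planned: *d*/75, if missing is dropped, shown apart or placed under not related
- Row that also counts possible: (*d* + *p* + *m*)/75

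| *d*, *p*, *m* | Table 6.2 | Table 6.7 related | Possible also counted |
|---|---|---|---|
| 2, 0, 0 | 2/75 = 2.7% | 2/75 = 2.7% | 2/75 = 2.7% |
| 2, 2, 0 | 2/75 = 2.7% | 2/75 = 2.7% | 4/75 = 5.3% |
| 2, 5, 0 | 2/75 = 2.7% | 2/75 = 2.7% | 7/75 = 9.3% |
| 2, 10, 0 | 2/75 = 2.7% | 2/75 = 2.7% | 12/75 = 16.0% |
| 2, 0, 2 | 4/75 = 5.3% | 2/75 = 2.7% | 4/75 = 5.3% |
| 2, 5, 2 | 4/75 = 5.3% | 2/75 = 2.7% | 9/75 = 12.0% |

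Exact (Clopper-Pearson) 95% limits show how imprecise such figures are: 0.3% to 9.3% for 2/75, and 8.6% to 26.3% for 12/75. With no possible and no missing ratings, nothing changes.

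**Step 4: what does not depend on relationship?** The safety endpoint (SAP 4.4, Table 6.1), deaths, and Tables 6.3 to 6.5 do not use the rating.

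**The case against.** The strongest reply is that the SAP applies the protocol's own cut. Protocol 9.4 limits device-related to definite and probable, and where to draw that line is a convention. The protocol does not say how many columns the relationship table must have, so two columns on the same cut can be called compatible with it. The second half of the definition of possible, that causality is unclear or lacking, makes leaving it out of a related count defensible. All of this stands as a defence of the cut, and a reader should not infer that the SAP invented it. It does not justify printing uncertain events as not related in a table the protocol asked for by relationship, after defining five levels.

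A reader might also infer that device-related harm is understated. The documents do not show that. There are no counts by relationship, and the missing rule works the other way in Table 6.2, where it raises the count. In Tables 6.6 and 6.7 its direction is undefined.

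Nor do the documents support saying that the tables cannot be reconciled. They diverge only if ratings are missing, and protocol 8.5 makes relationship part of every adverse event record. The table shells are present only as headings, so a missing column in them cannot be ruled out.

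Finally, possible events are not lost. They are counted in Table 6.3, SAP 5.1 puts all collected data in the listings, and under protocol 14.9 an independent Medical Monitor reviews serious events and their classification as device-related. That limits the consequence, although listings give no rates by organ class or preferred term.

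**Conclusion.** The point holds as a reporting weakness in descriptive safety tables. SAP 13.1 labels possibly related events as not related in Tables 6.6 and 6.7, a collapse that protocol 9.4 does not state. It also gives missing ratings a class in Table 6.2 and none in the other two. Device-related events can be under-reported in the device-related row of Table 6.2 (through possible) and in Tables 6.6 and 6.7 (through possible and, depending on handling, missing).

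The size is unknown. With 2 of 75 subjects rated definite or probable and none missing, it runs from no change to 2.7% against 16.0% as the assumed number rated possible goes from 0 to 10. Sample size, alpha, power and the safety endpoint are not affected. The change is worth making because the trial has no control arm and the data are already collected.

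**What to change.** In SAP 13.1:

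1. Show all five protocol categories plus a missing column in Tables 6.6 and 6.7. In Table 6.7, place each subject at the highest relationship. Rank missing between probable and possible; otherwise a subject with one possible and one missing event drops out of the subtotal in item 2.
2. Wherever a related subtotal is given, apply the Table 6.2 rule: definite, probable or missing.
3. Keep the existing Table 6.2 row, which already includes missing, and add one sensitivity row: definitely, probably or possibly related, or missing.
4. In SAP 3.5, record the departures from protocol 9.4: the missing-as-related rule, the added row, and any two-class grouping that is kept. Add a sentence squaring the missing rule with SAP 5.3, which rules out imputation for safety outcomes.

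The cost is a few columns and one row, with no new data. The protocol's definite/probable cut stays in place. The added figure will be less favourable if any subject's only candidate events are rated possible.
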